#### **4.9 Secondary Endpoints: Clinical Endpoints [DIARY1] (PEP and ITT)**

Many of the clinical endpoints rely on data collected on diary cards completed by the study participants. The subjects are asked to complete these twice a day (at 8AM and 8PM) on Days 0 through 14 and then again on Day 28. Fever is recorded for the preceding 12 hour period at both times each day, and symptoms are recorded at both times for Days 0 to 7 and then once daily on Days 8 to 14. Functional status (based on the Physical Function domain questions from the SF-36) and two questions giving a global assessment of status are completed daily at 8AM.

- a. Duration of clinical symptoms. Duration of clinical symptoms is defined as the time from Day 0 to the first of two successive measurements at which all clinical symptoms are grade 0 (absent) or 1 (mild). A measurement is considered to be the 8AM or 8PM assessment during Days 0 to 7 (so two measurements are obtained per day) and then the daily assessment thereafter. Time will then be calculated in half-days through to Day 7. For the purposes of defining the endpoint, if the subjects' first two assessments on (baseline assessment and first subsequent diary card assessment) satisfy this criterion, then the duration will be set to zero. Missing values will be ignored [this is equivalent to assuming that a missing value would have (a) indicated at least one grade 2+ symptom if the preceding record includes a grade 2+ symptom or if the first Day 0 value is missing; (b) indicated no grade 2+ symptoms if the preceding and succeeding assessments show no grade 2+ symptoms; and (c) indicated a grade 2+ symptom if the preceding assessment shows no grade 2+ symptom and the succeeding value shows a grade 2+ symptom]. Times will be considered as discrete (i.e. based on the schedule of completion of diary cards) and subjects not having two succeeding assessments with only grade 0 or 1 symptoms at any time during follow-up will be censored immediately after Day 14 (the last scheduled measurement time on which an endpoint can occur).
- Kaplan-Meier plot (and associated table) of the percent of subjects without clinical symptoms per the above definition over time, with the median duration of time to alleviation of such symptoms and its 95% confidence interval.
  - P-value comparing randomized arms from the log rank test.
  - Sensitivity analyses assuming (a) that missing values would include grade 2+ symptoms, (b) that missing values would not include grade 2+ symptoms, (c) that missing values would include grade 2+ symptoms in one randomized arm and would not include grade 2+ symptoms in the other arm (so as to maximize the difference between arms), and (d) the opposite of (c) (so as to minimize the difference between arms).

Note: Secondary analyses restricting to those with at least one grade 2 (moderate) or grade 3 (severe) clinical symptom based on the Diary Card at randomization, will be conducted for section a described above.

- b. Absence of fever Time to the absence of fever is defined as the time from Day 0 to the first of two successive assessments (through to Day 7) or the first assessment (Day 8 to Day 28) at which no fever  $\geq 38.0^{\circ}\text{C}$  is reported during the prior 12 hours and no antipyretics have been taken during the 24 hours. Time will then be calculated in half-days through to Day 7. For the purposes of defining the endpoint, if the first two assessments on Day 0 or 1 satisfy this criterion, then the duration will be set to zero. Missing values will be ignored [this is equivalent to assuming that a missing value would have (a) indicated fever if the preceding record includes fever or if the first Day 0 value is missing; (b) indicated no fever

if the preceding and succeeding assessments show no fever; and (c) indicated fever if the preceding assessment shows no fever and the succeeding value shows fever]. Times will be considered as discrete (i.e. based on the schedule of completion of diary cards) and subjects not having a 24-hour period without fever at any time during follow-up will be censored immediately after Day 14 (the last scheduled measurement time on which an endpoint can occur).

- Analysis for duration of fever will follow the same approach as for duration of clinical symptoms.
- c. Resolution of Symptoms and Fever. Time to resolution of all symptoms AND Fever is defined as the time from Day 0 to the first of two successive measurements at which all clinical symptoms are grade 0 (absent) or 1 (mild) and no fever  $\geq 38.0^{\circ}\text{C}$  is reported during the prior 12 hours and no antipyretics have been taken during the 24 hours.
- Analysis for duration of clinical symptoms and fever will follow the same approach as for duration of clinical symptoms.
- d. Global assessment: Times to “feeling as good as you did before you had the flu” and “functioning as well as you did before you had the flu” will be defined as the times of two successive measurements with “yes” responses to the respective global assessment questions.
- The details of the definition, handling of missing values and analysis will follow that for duration of clinical symptoms.
- e. Functional status: This is assessed using the 10-item domain of Physical Function from the SF-36, and calculated as the average of the scores of all 10 items. Functional status is evaluated daily through to Day 14 and then at Day 28.
- Scoring, including handling of missing values, will be undertaken per the standard instructions for the RAND 36-Item Health Survey 1.0 instrument (located at: [http://www.rand.org/health/surveys\\_tools/mos/mos\\_core\\_36item\\_scoring.htm](http://www.rand.org/health/surveys_tools/mos/mos_core_36item_scoring.htm) 1). If all 10 components are not scored, the pre-illness functional status will be scored as missing.
  - Figure and associated Table: Median, 25th and 75th percentiles, (and min and max value in table), with sample size, at each required measurement time.
  - Figure and associated Table: Median, 25th and 75th percentiles, (and min and max value in table), with sample size, change from Day 0 at each required measurement time.

- Statistical comparison between randomized arms of changes in score will be undertaken at Days 3, 7, 14 and 28 using Wilcoxon's test.
  - Time to return of physical function to pre-illness level is defined as the time from Day 0 to the first of two successive measurements at which the physical function score equals or is better than the pre-illness score (obtained by recall at enrollment). Time will be calculated in daily increments through to Day 14. For the purposes of defining the endpoint, if a subject's Day 0 and Day 1 assessments satisfy this criterion, then the duration will be set to zero. Missing values will be ignored. Times will be considered as discrete (i.e. based on the schedule of completion of diary cards) and subjects not having two successive assessments with scores equal to or better than the pre-illness score will be censored immediately after Day 14 (the last scheduled measurement time on which an endpoint can occur).
  - Kaplan-Meier plot (and associated table) of the percent of subjects returning to pre-illness level per the above definition over time, with the median duration of time to return and its 95% confidence interval.
  - P-value comparing randomized arms from the log rank test.
- f. The following outcomes are targeted in the protocol:
- Bronchitis / bronchiolitis
  - Pneumonia
  - Other complications

For each of these, the percentage of subjects experiencing the event during follow-up will be obtained with the associated 95% confidence interval and comparison of arms will be based on the normal approximation to the binomial distribution, or exact methods based on the binomial distribution if numbers are small.

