7.3 Efficacy Evaluations

7.3.1 Diary Card for Fever, Symptoms, and Functional Assessment

Subjects will maintain a diary card, and will be asked to make an entry twice daily (approximately 8AM and 8PM) through Day 7, and then every evening from Day 8 through 14. The subject completes the final diary card at the time of the final visit on Day 28.

On Day 0, subjects will be instructed on the diary card, and the initial (baseline) assessment will be completed by the study team and collected. Additionally, for the SF-36 physical domain, subjects will be asked to recall their status prior to enrollment.

At each subsequent study visit, the diary card for the day(s) since the last visit will be reviewed and collected. This diary will contain the information listed below (Section 7.3.1.1 – 7.3.1.4). However, any influenza symptoms listed on the diary cards will not be captured as adverse events for this study in accordance with section 8.3.1 of this protocol.

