7.3.1.1 Fever

Subjects will be asked to measure temperature orally at the time of completing the diary card and at anytime for symptoms of feverishness, and will be asked to record the maximal temperature since the time of entry for the previous diary card).

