7.3.1.3 Functional Status

The 36-item Health Survey (SF-36 v1) is a frequently used health survey used for multiple disease states. [27] This study will assess the 10-item domain of physical function (specifically, questions 3-12 of the SF-36 v1) (see Table 5), and subjects will be asked to note the response once each study day (approximately 8PM – reflecting the function during that day). These include (as originally numbered in the SF-36 v1):

Table 5: SF-36 Physical Function Domain Questions

| Question | Yes, Limited a Lot | Yes, Limited a Little | No, Not limited at All |
|--|--------------------------|-----------------------------|------------------------------|
| 3. Vigorous activities, such as running, lifting heavy objects, participating in strenuous sports | [1] | [2] | [3] |
| 4. Moderate activities, such as moving a table, pushing a vacuum cleaner, bowling, or playing golf | [1] | [2] | [3] |
| 5. Lifting or carrying groceries | [1] | [2] | [3] |
| 6. Climbing several flights of stairs | [1] | [2] | [3] |
| 7. Climbing one flight of stairs | [1] | [2] | [3] |
| 8. Bending, kneeling, or stooping | [1] | [2] | [3] |
| 9. Walking more than a mile | [1] | [2] | [3] |
| 10. Walking several blocks | [1] | [2] | [3] |
| 11. Walking one block | [1] | [2] | [3] |
| 12. Bathing or dressing yourself | [1] | [2] | [3] |

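### SAP 4.9 conflicts with the protocol's diary schedule, and with itself on the last fever event day; on its stated grid the fever sensitivity analyses would impute morning entries that were never scheduled

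*SAP*

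**What the plan says.** **Schedule.** Protocol 7.3.1 asks for diary entries "twice daily (approximately 8AM and 8PM) through Day 7, and then every evening from Day 8 through 14", with a final card at the Day 28 visit. SAP 4.9 opens by saying participants are "asked to complete these twice a day (at 8AM and 8PM) on Days 0 through 14" and again on Day 28. It then reduces symptoms to once daily after Day 7, but not fever: "Fever is recorded for the preceding 12 hour period at both times each day".

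**Look-back.** Protocol 7.3.1.1 has participants "record the maximal temperature since the time of entry for the previous diary card", which is about 24 hours once cards are evening-only. Protocol 3.3.3 defines absence of fever over 24 hours without an antipyretic. SAP 4.9b asks for two successive clear assessments through Day 7, "or the first assessment (Day 8 to Day 28) at which no fever" is reported in the preceding 12 hours, in both cases with no antipyretic in 24 hours.

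**Censoring.** In the same item, "subjects not having a 24-hour period without fever at any time during follow-up will be censored immediately after Day 14", on the ground that no endpoint can fall later.

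**Functional items.** According to the SAP, SF-36 function and "two questions giving a global assessment of status are completed daily at 8AM". Protocol 7.3.1.3 places the SF-36 items at about 8PM, "reflecting the function during that day". Protocol 7.3.1.4 gives no hour for the global questions.

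**Missing values.** The main analyses ignore them. Items b and c adopt the approach of item a, which adds four sensitivity scenarios: (a) all missing entries unfavourable, (b) all favourable, (c) unfavourable in one arm and favourable in the other so as to maximise the difference, and (d) the reverse of (c).

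**The concern.** A missing-value scenario needs a list of expected entries, and the only diary schedule written out in the SAP is the one that opens 4.9. SAP section 3 selects diary records by the study day on the CRF, but it does not say which morning and evening slots are expected on each day. A programmer who builds the grid from 4.9 will count as missing some entries that the protocol never requested.

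The scenarios are there to show how far genuinely missing diaries could move the result. On the wrong grid they would also show the effect of slots that are empty by design. Under c and d those slots are filled in opposite directions in the two arms, so part of any apparent sensitivity would come from the schedule and not from the data. Separately, item b leaves unclear whether a first clear card on Day 28 is an event or a censored time.

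**Working it through.** No stated figure is involved, so the check lists both schedules and applies the rules to constructed participants. Day d at 8AM is written d.0 and at 8PM d.5.

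**Entries per participant**
- Protocol 7.3.1: 8 days x 2 (Days 0-7) + 7 evenings (Days 8-14) + 1 (Day 28) = 16 + 7 + 1 = 24.
- SAP 4.9 opening paragraph: 15 days x 2 (Days 0-14) + 1 (Day 28) = 30 + 1 = 31.
- Difference: 31 - 24 = 7, namely the 8AM entries on Days 8 to 14.

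**Fever rule of 4.9b.** Each constructed participant completes every card the protocol asks for, is febrile on each card before a given time and clear from then on, and takes no antipyretic. The event is the first of two successive clear entries through Day 7, or one clear entry from Day 8.

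| First clear card | Missing ignored, either grid | Protocol grid, any scenario | SAP grid, missing = fever | SAP grid, missing = no fever |
|---|---|---|---|---|
| 3.0, 6.5 or 7.0 | unchanged | unchanged | unchanged | unchanged |
| 7.5 | 7.5 | 7.5 | **8.5** | 7.5 |
| 8.5 | 8.5 | 8.5 | 8.5 | **8.0** |
| 12.5 | 12.5 | 12.5 | 12.5 | **8.0** |
| never | censored | censored | censored | **event at 8.0** |

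The 8.0 values arise because the empty Day 8 morning slot, once set to no fever, meets the one-assessment rule by itself. The 8.5 arises because the same slot, set to fever, separates the clear Day 7 evening card from the clear Day 8 evening card. Scenarios c and d apply one of the last two columns to one arm and the other column to the other arm.

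**Composite of 4.9c** (two successive clear measurements throughout). On the twice-daily grid with missing = fever, every evening card from Day 8 follows an imputed febrile morning. A participant first clear at 7.5, 8.5 or 10.5 then has no two successive clear entries within Days 0-14 and is censored. The one possible exception is at 14.5, if the Day 28 card is counted as the successor of the Day 14 evening card. With missing = no fever, 8.5 becomes 8.0 and 10.5 becomes 10.0. All this requires the composite to be built on the fever grid. Item a's own definition of a measurement is daily after Day 7, and a composite built on that would avoid the problem.

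**Day 14 against Day 28.** In item a the event is the first of two successive measurements, so Day 14 (confirmed on Day 28) can be the last event time and censoring after Day 14 is coherent. In item b one clear assessment is enough as late as Day 28, so the same censoring sentence does not fit. Suppose Day 28 events are kept and everyone else is censored after Day 14. Then n participants remain at risk on Day 28 and all n have the event. The Kaplan-Meier factor is 1 - n/n = 0, so the curve reaches 100% resolved whatever happened to those censored.

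**Functional time.** SAP 4.9e counts return of physical function in whole days. Day k stays Day k whether it is labelled 8AM or 8PM, so the shift is 0. The global questions inherit item a's half-day clock. A half-day relabelling there moves both arms by 0.5 day; in a simulated two-arm example the log-rank p-value was 0.0473 before and after.

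**The case against.** The strongest reply is that little changes in practice. The main fever analysis is the same on either grid. Item b already follows the protocol's pattern in two respects, since it counts half-days only through Day 7 and switches to one assessment from Day 8. A clear evening card covers about 24 hours, so it satisfies a 12-hour look-back as well, and the derived time agrees with protocol 3.3.3. The sensitivity effect appears only if someone creates slots for cards that were never due. All of this stands, and it limits the point to sensitivity analyses of secondary endpoints. It does not remove the point: the SAP expressly affirms morning fever entries after Day 7, and nothing in it tells the programmer to disregard them.

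Three stronger readings are tempting and are not supported.

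- A reader might infer that the 8AM label places functional recovery 12 hours early. The SF-36 time is in whole days, so it does not move. For the global questions the protocol states no hour, and any shift would be common to both arms, so it should not be set against a between-arm benefit.
- A reader might infer that everyone unresolved after Day 7 becomes resolved when missing means no fever. The rule also requires 24 hours without antipyretics, and the SAP does not say that antipyretic use is imputed as absent.
- A reader might turn the seven slots into a number of participants affected per arm. Neither document gives the share unresolved after Day 7, and participants resolved by Day 7 AM cannot change.

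**Conclusion.** The point holds as a contradiction in the SAP with a conditional consequence. The SAP and protocol disagree on diary frequency for Days 8-14, on the period each fever entry covers, and on the hour of the SF-36 items. Item b disagrees with itself on the last day a fever event can occur.

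The size is seven unscheduled fever entries per participant if the SAP's grid is used. With missing = no fever, participants still febrile after Day 7 and off antipyretics become events at 8.0, in one arm only under c and d. With missing = fever, a Day 7 PM resolver moves from 7.5 to 8.5, and in the composite built on that grid no event from Day 7 PM onward can be reached within Days 0-14. This rests on two assumptions: that the grid is taken from the opening of 4.9, and that empty slots count as missing. The number of participants affected cannot be derived from the documents. The main fever analysis, the primary endpoint, power and alpha are unaffected. It should be corrected because a stated rule, followed as written, gives a wrong sensitivity result.

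**What to change.** 1. Rewrite the opening paragraph of SAP 4.9 to match protocol 7.3.1, 7.3.1.1 and 7.3.1.3: fever twice daily through Day 7 and evenings only on Days 8-14, each entry covering the time since the previous card, with SF-36 function at about 8PM. State the hour of the global questions.
2. In 4.9b and 4.9c, define the Day 8-14 look-back as the time since the previous card, consistent with the 24-hour definition in protocol 3.3.3. In 4.9c, state that a measurement from Day 8 is one evening card.
3. In 4.9b, make the last possible event time and the censoring time the same day.
4. State that the sensitivity scenarios impute only cards the protocol schedules, and say how antipyretic use is handled on an imputed card.

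With the protocol grid, a participant who completed every scheduled card has nothing to impute and all four scenarios return the same fever time. The cost is SAP wording and a small change to the derivation; no new data are needed.

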3.3.3 Endpoint Definitions

- Duration of viral shedding as assessed by PCR is defined as time to reduction of qPCR to below limit of detection, at the first of two successive measurements.
- Development of resistance is defined as the percentage of subjects who develop a resistant strain population by day 7, as measured by RNA sequencing of NA for recognized oseltamivir resistance mutations (e.g., H275Y or N295S in N1, R292K or E119V in N2).
- Duration of clinical symptoms is defined as the time to alleviation of all clinical symptoms to 0 (absent) or 1(mild) on two successive measurements in absence of symptom relief medications.
- Absence of fever (temperature <38.0°C/100.4°F) for 24 hours without antipyretic.
- Time to resumption of normal activity is defined as time to the time to the first “yes” answer to the global assessment question “Are you functioning as well as you were before you had the flu?” (Section 7.3.1.4).

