5.7 Concomitant Medications

Subjects will be monitored throughout the study for use of concomitant medications. Any prescription medications, over-the-counter (OTC) preparations, herbal remedies, and/or nutritional supplements taken during the study period must be recorded on the source document and in the eCRF.

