6 STUDY PROCEDURES

The following table (Table 4) outlines all of the assessments to be conducted during the study. A detailed presentation of assessments immediately follows the table. Total volumes of blood drawn are noted in the text for each study day. Details regarding the research samples (tubes, swabs, etc) will be detailed in the Manual of Procedures. The day when the subject is enrolled and randomized is denoted as Study Day 0, the first day after randomization is Study Day 1, etc.

Table 4: Schedule of Assessments

| Day +/- Window Evaluation/Procedure | Screen | Baseline | | | | | |
|--|---------------|-----------------|--------|--------|---|-------|--------|
| | -1 to 0 | 0 | 1 Home | 2 Home | 3 | 7 ± 1 | 28 ± 3 |
| ELIGIBILITY | | | | | | | |
| Informed consent | X | | | | | | |
| Demographics | X | | | | | | |
| Medical history | X | | | | | | |
| Site influenza testing (PCR or rapid Ag, See Section 7.2.2) | X | | | | | | |
| RANDOMIZATION/ STUDY DRUG | | | | | | | |
| Randomize subject | | X | | | | | |
| Dispense Study Treatment Kit | | X | | | | | |
| STUDY PROCEDURES | | | | | | | |
| Review and collect diary card (see Section 7.3.1) | | X ¹ | | | X | X | X |
| Assess for complications of influenza (see Section 7.3.2) | | X | | | X | X | X |
| Vital signs, including SaO ₂ (see Section 7.3.3) | X | X | | | X | X | X |
| Assessment of study drug compliance (see Section 7.5) | | | | | X | | |
| Review of concomitant medications | | | | | X | X | X |
| Physical exam ² (see Section 7.1.2) | X | | | | X | X | X |
| Adverse events | | | | | X | X | X |
| SAFETY LABORATORY | | | | | | | |
| Urine βHCG (for females of childbearing potential) | X | | | | | | |
| REFERENCE PROCEDURE | | | | | | | |
| Nasopharyngeal swab for virus isolation | | X | | | X | X | |
| Subject sample self-collection (see Section 6.3.3.2) | | X | X | X | X | | |
| Stored Serum | | X | | | X | X | X |

Notes: 1. On Day 0, subject will be instructed on how to complete the diary card, and baseline assessment will be collected.

2. Brief physical examinations will be conducted at screening to ensure there are not medical conditions (either chronic or acute) that would increase a subject's risk for participation in this study. Symptom-targeted physical examinations will be conducted at all other visits as needed to evaluate new complaints and possible adverse events.

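### SAP 4.9a omits the protocol's medication-free condition, so time to alleviation of symptoms is defined differently in the two documents

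*SAP*

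**What the plan says.** Protocol 3.3.3 defines duration of clinical symptoms, the basis of the secondary endpoint time to alleviation, with two requirements. Every symptom must be scored 0 or 1, and this must hold "on two successive measurements in absence of symptom relief medications".

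SAP 4.9a keeps the grade threshold and the two-assessment rule. The event is the "first of two successive measurements at which all clinical symptoms are grade 0 (absent) or 1 (mild). A measurement is considered to be" the morning or evening entry through Day 7 and the daily entry after that. The zero-duration rule applies the same grade criterion to the first two assessments: "baseline assessment and first subsequent diary card assessment) satisfy this criterion, then the duration will be set to zero".

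Three other provisions bear on the point:

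- **SAP 4.9c.** "Time to resolution of all symptoms AND Fever is defined as the time from Day 0 to the first of two successive measurements" with symptoms absent or mild, no fever, and "no antipyretics have been taken during the 24 hours". Item b has the same antipyretic condition.
- **Note under SAP 4.9a.** "Secondary analyses restricting to those with at least one grade 2 (moderate) or grade 3 (severe) clinical symptom" at randomization are planned. The note does not mention medication.
- **Data on medication.** Under Protocol 5.7, prescription and over-the-counter products "taken during the study period must be recorded on the source document and in the eCRF". Table 4 in Protocol section 6 schedules "Review of concomitant medications" at Days 3, 7 and 28.

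On resumption of normal activity, Protocol 3.3.3 uses the first *yes* to the functioning question. SAP 4.9d uses two successive *yes* answers.

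**The concern.** Time to alleviation of symptoms is the first clinical secondary endpoint listed in Protocol 3.3.2, and SAP 4.9a gives it a Kaplan-Meier analysis and a log-rank p-value. If the SAP is followed as written, the result carries the protocol's name but answers a different question: time until symptoms are mild with or without relief medication, rather than time until they are mild without it. No planned analysis reports the protocol's version. If the mismatch is noticed only after arm comparisons have been seen, whichever definition is then chosen will be open to challenge.

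**Working it through.** The documents state no figure for this endpoint, so there is nothing to reproduce. The check is a comparison of the rules, followed by traces on assumed subjects.

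**1. Rule by rule**

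| Element | Protocol 3.3.3 | SAP 4.9a |
|---|---|---|
| Grade | all 0 or 1 | all 0 or 1 |
| Persistence | two successive | two successive |
| Relief medication | must be absent | not mentioned |
| Zero duration | not given | grade only |
| Missing values, censoring | left to the SAP | grade only |
| Sensitivity analyses | left to the SAP | missing diary values only |

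**2. Direction for one subject.** Let G(k) mean that grades qualify at assessment k, and M(k) that relief medication was used in the look-back before k.

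- SAP time: the first k with G(k) and G(k+1).
- Protocol time: the first k with G(k), G(k+1), not M(k) and not M(k+1).

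Every pair that satisfies the protocol also satisfies the SAP, so SAP time ≤ protocol time. The two are equal if no medication is used. They are also equal if medication starts only after a qualifying unmedicated pair: with symptoms mild from 2.0 and doses only on Days 5 and 6, both rules give 2.0.

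**3. Illustration, all inputs assumed.** Days are in halves (8AM = .0, 8PM = .5). Subject A has a moderate or severe symptom at baseline, is absent or mild from 2.0, and takes one relief dose daily, the last on Day 3. SAP 4.9a gives 2.0. The protocol states no look-back, so its time depends on the convention:

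| Look-back | Status of assessments | Protocol time |
|---|---|---|
| Since previous entry, 7AM dose | 3.0 medicated; 3.5 and 4.0 clear | 3.5 |
| Calendar day | Day 3 medicated; 4.0 and 4.5 clear | 4.0 |
| 24 h, 8AM dose, a dose exactly 24 h earlier counts | 4.0 medicated; 4.5 and 5.0 clear | 4.5 |
| Same, exact 24 h does not count | 4.0 and 4.5 clear | 4.0 |
| 24 h, 10PM dose | 4.0 (10 h) and 4.5 (22 h) medicated; 5.0 (34 h) and 5.5 clear | 5.0 |

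For this subject the gap is 3.5 − 2.0 = 1.5 to 5.0 − 2.0 = 3.0 days. Subject B is absent or mild from baseline, with the same daily use starting before baseline. The SAP sets B to 0, while the protocol condition gives the same column, 3.5 to 5.0. These are single histories, not bounds and not differences between arms.

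**4. Do other analyses cover the gap?** If A is afebrile and the 8AM drug is an antipyretic, 4.9c gives 4.5 (4.0 if a dose exactly 24 h earlier does not count). If the drug is not an antipyretic, 4.9c gives 2.0, the same as 4.9a. The symptom list in Protocol 7.3.1.2 includes cough, nasal obstruction, rhinorrhea and diarrhea, for which relief need not be an antipyretic. The baseline grade 2 or 3 analysis keeps A at 2.0. It removes B because of the baseline grade, not because B was medicated.

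**5. Functioning question.** Take daily answers for Days 0 to 7 of no, no, no, no, yes, no, yes, yes. The first *yes* is Day 4, and the first of two successive is Day 6. With a steady *yes* the rules agree if the SAP means the first of the pair, and differ by one day if it means the second. Item d refers to the times of two measurements and points to 4.9a for details, so first-of-two is only an inference.

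**The case against.** **The protocol's condition cannot be applied as written.** It names no drugs, look-back or data source. Protocol 9 and 9.4 leave analysis details to the SAP, the diary contents in Protocol 7.3.1 include no medication item, and the documents do not say that intake times are recorded. This stands as an argument about which version should be the main one. It does not explain why the SAP neither applies the condition nor reports a version with it, when 4.9b and 4.9c already assume antipyretic information at 24-hour resolution.

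**The change may already be declared.** The SAP contents page lists an introduction and a key-updates section that are not in the text available, so a stated reason cannot be excluded. The operative definitions would still differ. The SAP's own notes on resumption of normal activity name the three measures to be used, but do not mention the move to two *yes* answers.

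**Readings the documents do not support.** A reader might infer that the omission favors one arm or dilutes the treatment effect. Neither follows: no medication use by arm is given, a shift in both arms need not change the difference, and a simulation would only return its assumed inputs. A reader might also take the traced 1.5 to 3.0 days as the size of the error, but they depend on the invented history and the chosen look-back. Finally, the baseline grade 2 or 3 analysis might be read as mitigation. It contains no medication condition, so it is not.

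**Conclusion.** The mismatch is established from the text and rests on no assumed figure. SAP 4.9a omits a condition that Protocol 3.3.3 makes part of the endpoint, and only 4.9c offers partial cover, for antipyretics and for a different endpoint. For each subject the SAP time is equal to or earlier than the protocol time, provided all other rules are the same. The size and direction of any effect on the arm comparison are unknown. The matter is confined to secondary endpoints: it is worth correcting but does not threaten the primary analysis. The rule for the functioning question is a minor inconsistency of the same kind.

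**What to change.** Reconcile Protocol 3.3.3 and SAP 4.9a before treatment comparisons are seen:

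1. Name the main definition in the SAP and report both versions: the protocol's, with the medication condition also applied under the zero-duration rule, and the medication-agnostic one.
2. State the data source: either the source behind the antipyretic condition in 4.9b and 4.9c, which the SAP does not identify beyond its diary table tag, or the concomitant medication eCRF.
3. State which recorded drugs count, and a look-back the data can support (the calendar day if intake times are not recorded).
4. If the missing front section already declares the change, still add the protocol-definition analysis.
5. For 4.9d, choose one rule for the functioning question, say whether the time is that of the first of the two answers, and report the other rule as supportive.

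The cost is SAP wording, a drug list and a derived flag, with no new data collection if a coarse flag is accepted. That flag is weakest for Days 8 to 14: after Day 7 the next scheduled review is Day 28, which is 28 − 14 = 14 to 28 − 8 = 20 days later on the nominal schedule. Subjects who keep medicating before reaching two successive unmedicated qualifying assessments will have later or censored times. How many is not known from the documents.
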